### Medication Titration & Taper.

Participants will have four weeks of up-titration: one tablet daily (Naltrexone 8mg/ Bupropion 90mg; 1 week), then two tablets daily (Naltrexone 16mg/ Bupropion 180mg; 1 week), then three tablets daily (Naltrexone 24mg/ Bupropion 270mg; 1 week), to reach the full dose of four tablets daily (Naltrexone 32mg/ Bupropion 360mg).

If participants drop out of the study during, we will ask that they return any unused medication. Participants who have been on the study medication for more than 4 weeks, including those who complete the treatment, will be asked to taper off the study medication: two tablets daily (Naltrexone 16mg/ Bupropion 180mg; 4 days), then one tablet daily (Naltrexone 8mg/ Bupropion 90mg; 3 days), to discontinue medications. Participants on placebo will take the same number of tablets as the active group to maintain the blind. Participants will be cautioned against stopping the medication abruptly. Taper off is not medically necessary for participants on the study medication for 4 weeks or less.

- 12. **Data and Safety Monitoring Plan:** Include an appropriate Data and Safety Monitoring Plan (DSMP) based on the investigator's risk assessment stated below. (Note: the HIC will make the final determination of the risk to subjects.)
  - a. What is the investigator's assessment of the overall risk level for subjects participating in this study? Greater than minimal.
  - b. If children are involved, what is the investigator's assessment of the overall risk level for the children participating in this study? n/a
  - c. Include an appropriate Data and Safety Monitoring Plan. Examples of DSMPs are available here http://your.yale.edu/policies-procedures/forms/420-fr-01-data-and-safety-monitoring-plans-templates for
    - i. Minimal risk
    - ii. Greater than minimal

The principal investigators will be responsible for monitoring the data, assuring protocol compliance, and conducting the safety reviews semi-annually. Although this study qualifies as clinical trial research, it does not meet NIH criteria for Phase III clinical trial research. Nonetheless, this study will be monitored semi-annually by a Data Safety Monitoring Board (DSMB) as the study involves a double-blind placebo controlled evaluation of medication effects that may involve greater than minimal risk. Adequate surveillance and protections will be put in place to discover adverse events promptly and keep their effects to a minimum. During the review process, the principal investigators and DSMB will evaluate whether the study should continue unchanged, require modification/amendment, or close to enrollment. Either the principal investigator, the IRB or the DSMB have the authority to stop or suspend the study or require modifications.

The risks associated with the current study are deemed greater than minimal for the following reasons:

- 1. We do not view the risks associated with the NB combination medication as minimal risks.
- 2. Given the now established safety and validity of the current NB combination medication in RCTs and FDA approval, we do not view the proposed studies as high risk.

Although we have assessed the proposed study as one of greater than minimal risk, the potential exists for anticipated and/or unanticipated adverse events, serious or otherwise, to occur since it is not possible to predict with certainty the absolute risk in any given individual. Therefore, we provide a plan for monitoring the data and safety of the proposed study as follows:

#### DATA AND SAFETY MONITORING PLAN

The treatment interventions and assessment protocols are well-established and pose primarily low risks to subjects. The DSMP focuses on close monitoring by the PIs in conjunction with the study MDs. Excessive adverse events and/or any serious events (should they occur) will be reported promptly to the NIH and to the Yale Human Investigation Committee.

A Data and Safety Monitoring Board (DSMB) will monitor this project. The DSMB is composed of Yale investigators who are independent of the proposed trial and experienced in various aspects relevant to the current proposal including: conduct of clinical trials, biostatistics, primary care, and the clinical management of obesity and BED.

We have developed a standard DSMB report form that summarizes, on a semi-annual basis:

- 1. Recruitment, retention, and follow-up rates for the study and compares them to target rates.
- 2. Rates of data completeness and availability of primary outcome data
- 3. Occurrence of AEs and SAEs
- 4. Report of study progress since the last report.
- 5. Rates of recruitment of women and minorities with respect to targets.

These reports are generated by the study coordinator, signed by each study PI prior to their submission to the DSMB. DSMB comments are documented and forwarded to the Yale IRB at the time of the annual review and reapproval. They will also be summarized as part of the annual progress report to NIDDK. However, if adverse events occur in greater magnitude or frequency than expected these will be reported to the DSMB, HIC, and NIH prior to scheduled reports. The Principal Investigators ([name] & [name]) will assume full responsibility for reporting serious and non-serious and unanticipated adverse events. The DSMB may call an ad-hoc meeting to address emergent safety concerns.

Because the projected effect sizes may not be large enough for detection during interim analyses, we are not proposing a preliminary analysis of accumulating efficacy and safety data by treatment assignment. Instead, we propose to submit semi-annual reports of aggregate data to the DSMB members that contains screening data, baseline demographics, retention data, serious adverse events data, as well as accrual status including projections, times to milestones, and any other data that will help in the assessment of the clinical trial. Based on this report, each DSMB member will complete a form making one of two recommendations: 1) continue recruitment as planned; or 2) schedule formal DSMB meeting immediately. If any DSMB member recommends a meeting, this will be scheduled within one week, minutes will be kept, the report will be

reviewed with the PI, and the committee will vote on whether the study should: 1) continue recruitment unchanged; 2) continue with a protocol amendment; 3) stop recruiting pending further investigation. If, after this meeting, any DSMB member votes to stop recruitment or requests a protocol modification, the Yale IRB will be informed.

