### Measurement and reporting of adverse events.

Adverse event data will be collected on an on-going basis. These data will be collected and examined with blindness to the medication condition (Naltrexone/Bupropion or placebo). Adverse events data will be reviewed by the PI, co-investigators, and the DSMB throughout this trial (see Table below). A summary of adverse events will be provided to the Yale IRB yearly during the annual renewal review process. Any serious or unanticipated adverse events will be reported to the NIH and to the Yale IRB within 48 hours.

The frequency of data review is summarized in the following table:

Table	Data type	Frequency of Review by PIs and Research Team	Frequency of Review by PI and DSMB		
Table 1	Subject accrual	Monthly	Twice-yearly		
Table 2	Treatment completion rates (retention/attrition)	Twice-yearly	Twice-yearly		
Table 3	Adverse and serious adverse event rates	Twice-yearly	Twice-yearly		
Table 4	Checklist for DSMB	NA	Twice-yearly		

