### Procedures for providing follow up care:

Medical monitoring will occur at all clinic and follow up visits and medical care will be provided if warranted. If a study participant experiences any psychiatric symptoms or distress (e.g., depressive symptoms or

suicidality) at any stage of study participation he/she will receive short-term treatment and support from the study treatment team (including psychologists and a psychiatrist) and will be connected to a local emergency department (e.g., the Crisis Intervention Unit at Yale-New Haven Hospital) and his/her physician or therapist for ongoing care.

Measurement and reporting of subject accrual, adherence to inclusion/exclusion criteria.

Review of the rate of subject accrual and adherence to inclusion/exclusion criteria will occur regularly by the PI and co-Investigators and yearly by the DSMB. These reviews will help to assure that participants meet eligibility criteria and ethnic diversity goals outlined in the grant proposal.

Measurement and reporting of participant treatment completion rates.

Participation rates (retention and attrition) will be reviewed on an ongoing basis by the PIs and co-investigators to identify any potential problems, and formally by the PIs and DSMB semi-annually. Any differential dropout across blinded study groups and/or higher than expected dropout will be reviewed by the investigators to determine whether any problems are present and what, if any, corrective action needs to be taken.

During the reviews, if the DSMB has concerns about whether attrition has reached a level that might inhibit the ability of the study to address its primary aims, they will suggest a meeting to discuss methods for improving subject retention. Previous pharmacotherapy studies for BED (with comparable time frames for pharmacotherapy) have reported attrition rates between 20% and 38%. Studies of bupropion for obesity treatment reported attrition of 30% to 38%. Thus, "trigger points" for review and discussion by principal investigator and research staff will be: 35% ("low alert"), 40% ("mid alert"), 45% ("high alert"), 50% ("extreme alert"). With early alerts to problems, action would be taken to avoid higher level alerts; if a higher-level alert should arise, more drastic actions would be taken.

The following actions would be taken at each level of alert:

- (1) Low-level alert = Review of potential problems by PI.

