### 2. Limits of Assumptions

It is possible that baseline differences between the treatment conditions, excessive attrition, and/or missing data could limit the value of data analysis. Baseline differences across blinded treatment groups, if present, will be evaluated yearly and considered in relation to potential effects on the power to detect differences in the primary outcomes. If these effects were to develop and be sizeable, alterations to the randomization schedule would be considered. Any plans to alter the randomization scheme would be communicated to the NIH.

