### 3. Limits of Rules

There are other situations that could occur that might warrant stopping the trial and/or including a section on the safety report entitled "Other situations that have occurred since the last safety report that warrant discussion" to allow for communication of concerns.

Finally, as currently outlined above, the DSMB has the authority to stop the trial following any serious adverse event or following any semi-annual review of adverse events.

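### The DSMB gets only aggregate, blinded safety and retention reports with no stated route to data by arm, while investigators who must stay blind review dropout across masked groups

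*Combined protocol and SAP*

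**What the plan says.** All references are to the combined protocol and SAP, Section I.

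**What the DSMB receives.** Item 12, Data and Safety Monitoring Plan, rules out an interim look by arm ("we are not proposing a preliminary analysis of accumulating efficacy and safety data by treatment assignment") because the projected effects may be too small to detect at that stage. In its place, "we propose to submit semi-annual reports of aggregate data to the DSMB members"; the listed content includes retention and serious adverse events. On preparation: "These reports are generated by the study coordinator, signed by each study PI prior to their submission to the DSMB". Under Measurement and reporting of adverse events, where the DSMB is among the reviewers, "These data will be collected and examined with blindness to the medication condition".

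**Who looks by group.** Under the heading on participant treatment completion rates, "Any differential dropout across blinded study groups and/or higher than expected dropout will be reviewed by the investigators". Retention is also reviewed "formally by the PIs and DSMB semi-annually", with no statement that the board sees it by group. Under Trial Stopping Rules, Limits of Assumptions: "Baseline differences across blinded treatment groups, if present, will be evaluated yearly". That section names no reviewer, and says sizeable effects could lead to changes in the randomization schedule.

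**Who must stay blind, and who can act.** Item 4 (treatment protocol for NB) keeps investigators and assessors blind until every participant has finished the 12-month follow-up. Limits of Rules states that "the DSMB has the authority to stop the trial following any serious adverse event" or after any semi-annual adverse event review. Item 12 gives the principal investigator and the IRB power to stop the study too.

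**The concern.** The protocol says it has a DSMB because this is a double-blind, placebo-controlled evaluation of a drug that may carry more than minimal risk. In such a trial the concurrent placebo arm is the best guide to whether an event is due to the drug. Under the written plan the board does not see that comparison. It must judge pooled rates against outside expectations.

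Those expectations are thin for half the sample. The protocol describes the large NB trials it cites as trials in obesity, and its own pilot (N=22) and ongoing trial are in BED with obesity. Half of the planned 200 have no obesity.

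The by-group reviews that the plan does contain (dropout and baseline) are not routed to the board. One goes to the investigators, who are meant to stay blind, and the other to nobody named. Someone has to hold the codes to build those comparisons, but no such preparer is identified.

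**Working it through.** The plan states no power calculation or projected effect size, so there is no figure of its own to reproduce beyond the sample size. The check asks whether a pooled report can conceal an imbalance that a table by arm would show.

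**Inputs**
- Four cells of 50, allocated 1:1: 4 × 50 = 200, so 100 per arm (items 1 and 4, Randomization).
- First attrition alert at 35%, with no trigger by arm (item 12, treatment completion rates).
- SAE rates in an earlier NB trial: 1.6% on NB, 1.4% on placebo (item 10).
- Nausea on NB: 32.5% (Section II, Risks).
- Two-sided 0.05, borrowed from item 13 as a yardstick only.
- Assumed here: the splits between arms, all 200 counted, and a placebo nausea rate of 5% to 20%.

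**Dropout.** 68/200 = 34.0%, below the 35% alert however it is divided:

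| Split (100 v 100) | Pooled | Fisher p |
|---|---|---|
| 34 v 34 | 34% | 1.00 |
| 42 v 26 | 34% | 0.025 |
| 44 v 24 | 34% | 0.004 |
| 48 v 20 | 34% | < 0.001 |

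The pooled figure cannot separate these rows.

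**Power by arm for dropout.** Power = Φ[(d − 1.96·se0)/se1]. For true rates of 44% v 24%, d = 0.20 and the mean rate is 0.34. Then se0 = √(0.34 × 0.66 × 2/100) = 0.0670 and se1 = √((0.44 × 0.56 + 0.24 × 0.76)/100) = 0.0655. Power = Φ[(0.20 − 0.1313)/0.0655] = Φ(1.05) ≈ 85%. The same formula gives about 56% with 50 per arm and 32% with 25 per arm, so early looks are much weaker.

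**SAEs.** Average rate (1.6% + 1.4%)/2 = 1.5%, so 200 × 0.015 = 3 are expected. For a binomial with n = 200 and rate 0.015, P(X ≥ 6) = 0.082, so six pooled SAEs are only mildly unusual. By arm, 3 v 3 gives Fisher p = 1.00 and 6 v 0 gives p = 0.029. The gain is limited: exact Fisher power at 100 per arm is about 15% for 5% v 1.4% and about 70% for 10% v 1.4%.

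**Common events.** For nausea at 32.5% against an assumed placebo rate of 5%, 10%, 15% or 20%, power by arm is above 99%, 98%, 83% and 52% with 100 per arm, and 95%, 79%, 54% and 29% with 50 per arm. Frequent events are where an arm comparison tells the board most.

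**The case against.** The strongest reply is that the trial is small, single-site and short, tests a marketed drug, and already has safeguards. Item 11 provides individual review of blood pressure, heart rate, liver tests and depressive symptoms, a BMI signal for participants without obesity, and an emergency code-break. Item 12 provides attribution of each event, 48-hour reporting of serious events, early reporting of excess events and ad hoc DSMB meetings. It also lets the DSMB report carry other helpful data. With about three SAEs expected, the low-power argument has some force for safety as well as efficacy.

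Much of this stands, and it limits how severe the point is. It does not close the gap. Individual safeguards cannot show an excess in one arm. The allowance for other data and the ad hoc meetings do not mention arm-level data, and the only report route written runs through the coordinator and the principal investigators. Low power is a reason not to test, but a descriptive table needs no test.

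Stronger readings are tempting and should be resisted:
- A reader might infer that investigators can see a safety imbalance hidden from the board. The documents give them dropout by masked group; adverse events are examined blind.
- A reader might infer that masked dropout codes reveal which arm is active. That is speculative: the term is undefined, most naturally means codes, and a group rate does not disclose anyone's allocation.
- A reader might infer that only the DSMB can stop the trial. The principal investigator and the IRB can as well.
- A reader might infer that NB had not been studied in BED. A pilot and an ongoing trial in BED with obesity are cited.

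**Conclusion.** The gap is real and worth correcting, but moderate. As written, the DSMB receives no safety or retention table by arm and has no stated way to obtain one, and the reason given does not support that for descriptive safety data. By-group reviews of dropout and baseline exist but sit with blinded investigators or an unnamed reviewer.

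The size is illustrative, not estimated. A 28-point dropout difference (48% v 20%) can sit under the first pooled alert, and six SAEs can conceal a 6 v 0 split. This rests on assumed splits and full enrolment of 100 per arm. The dropout example shows what the DSMB's stated report would miss, not what everyone would miss, since the investigators already look at dropout by masked group. Tables by arm would not reliably detect modest SAE excesses or speak clearly at early looks; their value lies mainly in discontinuations, common adverse events, vital signs and liver tests.

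**What to change.** Keep the ban on interim efficacy analysis. Amend item 12 (Data and Safety Monitoring Plan, adverse event reporting, treatment completion rates, Limits of Assumptions) as follows:

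1. A closed semi-annual report goes directly to the DSMB, prepared by the pharmacy code-holder or by a statistician separated from blinded staff. It describes adverse events, SAEs, discontinuations, blood pressure, heart rate and liver tests by coded arm and obesity stratum, without hypothesis tests.
2. The DSMB may ask to have the codes unmasked.
3. The open report, and everything shown to the investigators and coordinator, is pooled.
4. The reviews of dropout and baseline by group move into the closed report, with a named reviewer.

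**Cost.** One extra set of tables on an existing semi-annual cycle, and a preparer who must be kept apart from blinded staff. The Randomization section already places the schedule with the biostatistician and the Investigational Drug Pharmacy, so the codes need no new holder. If the trial biostatistician also advises the blinded team, someone else should prepare the report. No alpha is spent, because no efficacy data are shown. Tables by stratum will be sparse early on (at most 50 per cell) and should be read as such.

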### Measurement and reporting of adverse events.

Adverse event data will be collected on an on-going basis. These data will be collected and examined with blindness to the medication condition (Naltrexone/Bupropion or placebo). Adverse events data will be reviewed by the PI, co-investigators, and the DSMB throughout this trial (see Table below). A summary of adverse events will be provided to the Yale IRB yearly during the annual renewal review process. Any serious or unanticipated adverse events will be reported to the NIH and to the Yale IRB within 48 hours.

The frequency of data review is summarized in the following table:

Table	Data type	Frequency of Review by PIs and Research Team	Frequency of Review by PI and DSMB		
Table 1	Subject accrual	Monthly	Twice-yearly		
Table 2	Treatment completion rates (retention/attrition)	Twice-yearly	Twice-yearly		
Table 3	Adverse and serious adverse event rates	Twice-yearly	Twice-yearly		
Table 4	Checklist for DSMB	NA	Twice-yearly		

### Attribution of Adverse Events:

Adverse events will be monitored for each subject participating in the study and attributed to the study procedures by the investigators according to the following categories:

- a) Definite: Adverse event is clearly related to the investigational procedure/agent.
- b) Probable: Adverse event is likely related to the investigational procedure/agent.
- c) Possible: Adverse event may be related to the investigational procedure/agent.
- d) Unlikely: Adverse event is likely not to be related to the investigational procedure/agent.
- e) Unrelated: Adverse event is clearly not related to the procedure/investigational agent.

### Plan for Grading Adverse Events:

The following scale will be used in grading the severity of adverse events noted during the study:

- 1. Mild adverse event
- 2. Moderate adverse event
- 3. Severe adverse event

### Plan for Determining Seriousness of Adverse Events:

**Serious Adverse Events**: In addition to grading the adverse event, the PI will determine whether the adverse event meets the criteria for a Serious Adverse Event (SAE). An adverse event is considered serious if it results in any of the following outcomes:

- 1. Death;
- 2. A life-threatening experience in-patient hospitalization or prolongation of existing hospitalization;
- 3. A persistent or significant disability or incapacity;
- 4. A congenital anomaly or birth defect; OR

5. Any other adverse event that, based upon appropriate medical judgment, may jeopardize the subject's health and may require medical or surgical intervention to prevent one of the other outcomes listed in this definition.

An adverse event may be graded as severe but still not meet the criteria for a Serious Adverse Event. Similarly, an adverse event may be graded as moderate but still meet the criteria for an SAE. It is important for the PI to consider the grade of the event as well as its "seriousness" when determining whether reporting to the IRB is necessary.

Plan for events to the Yale IRB that are unexpected AND related AND involve risk of harm to subjects or others:

The PIs will report any incident, experience, or outcome that meets all three of these conditions to the IRB immediately:

- 1. Unexpected (in nature, specificity, severity, or frequency); given (a) the research procedures described in the protocol-related documents, such as the IRB-approved protocol and informed consent document and (b) the characteristics of the subject population being studied; AND
- 2. Related or possibly related to participation in the research (possibly related means there is a reasonable possibility that the incident, experience, or outcome may have been caused by the procedures involved in the research); AND
- 3. Suggests that the research places participants or others at greater risk of harm (physical, psychological, economic, legal, or social) than previously known or recognized.

Unanticipated Problems Involving Risks to Subjects or Others (UPIRSOs) may be medical or non-medical in nature, and include – but are not limited to – *serious, unexpected, and related adverse events* and *unanticipated adverse device effects*. Adverse events are reportable to the IRB as UPIRSOs only if they meet all 3 criteria listed above.

These UPIRSOs/SAEs will be reported to the IRB in accordance with IRB Policy 710, using the appropriate forms found on the website. All related events involving risk but not meeting the prompt reporting requirements described in IRB Policy 710 should be reported to the IRB in summary form at the time of continuing review and/or a current DSMB report. If appropriate, such summary may be a simple brief statement that events have occurred at the expected frequency and level of severity as previously documented.

Plan for reporting adverse events to co-investigators on the study, as appropriate the protocol's research monitors, e.g., study sponsors, funding and regulatory agencies, and regulatory and decision-making bodies: For the current study, the following individuals, funding, and/or regulatory agencies will be notified:

- i. All Co-Investigators listed on the protocol
- ii. National Institutes of Health

The investigators will conduct a review of all adverse events upon completion of every study subject. The investigators will evaluate the frequency and severity of the adverse events and determine if modifications to the protocol or consent form are required.

